11.1.2 Statistical methods, immunogenicity

• Primary analysis: calculate two-sided 95%CI for the difference in proportion seropositive at day 91.

 Secondary analyses: include calculation of 95% confidence intervals for seropositivity, seroconversion and geometric means as well as multivariable logistic and normal errors regression adjusting for covariates.

11.1.3 Statistical methods, safety

- Primary analysis: proportion (with 95% CI) with any adverse events in aerosol group and in subcutaneous group;
- Secondary analysis: proportions (with 95% CI) of individual adverse events.

11.2 Sample size

11.2.1 Immunogenicity

Total to be enrolled, 2000. Number available for primary analysis (after loss to follow up), 1600. These numbers are based on the following assumptions:

- Significance 2.5%, one-sided for non-inferiority, 5% two-sided for superiority;
- Non-inferiority margin 5%;
- Power for non-inferiority 90% if true seroconversion is 90% in both arms;
- 20% loss to follow up by day 91.
- Calculate two-sided 95%CI for difference in proportion seropositive at day 91. If lower limit of difference greater than -5% then conclude non-inferiority. If lower limit of difference greater than 0% then conclude superiority.

With 100 children sampled at random from those being followed up, based on a standard deviation of post vaccination titres of 0.43, differences of <1.5 fold in geometric mean titres between aerosol and subcutaneous groups between days 28 and 364 would be able to be detected at a 5% level with 80% power. Smaller differences between days 28 and 91, and 91 and 364 would also be detectable.

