7.2 Exclusion criteria

- Having received measles, measles-rubella or measles-mumps-rubella vaccine (with confirmation from vaccination card).
- Any contraindication to measles vaccine administration as stated in the WHO measles vaccine position paper: ⁴²
 - Persons with a history of an anaphylactic reaction to neomycin, gelatine or other components the vaccine should not be vaccinated.
 - Furthermore, measles vaccine is contraindicated in persons who are severely immunocompromised as a result of congenital disease, HIV infection, advanced leukaemia or lymphoma, serious malignant disease, or treatment with high-dose steroids, alkylating agents or antimetabolites, or in persons who are receiving immunosuppressive therapeutic radiation.
 - Administration of immunoglobulins or other antibody-containing blood products may interfere with the immune response to the vaccine. Vaccination should be delayed for 3–11 months after administration of blood or blood products, depending on the dose of measles antibody. Following measles vaccination, administration of such blood products should be avoided for 2 weeks, if possible.
 - Mild, concurrent infections are not considered a contraindication, and there is no evidence that measles vaccination exacerbates tuberculosis. However, vaccination should be avoided if there is high fever or other signs of serious disease.

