9.1 Primary outcome

Measles seropositivity at day 91 post-vaccination.

Measles seropositive specimens are:

• specimens tested by Enzygnost Anti-measles-virus/IgG (Dade-Behring, Marburg, Germany) enzyme-linked immunosorbent assay with optical density signal ≥ 0.1 , or

specimens tested by Enzygnost with optical density signal < 0.1, that are subsequently tested by plaque reduction neutralization test with a result of \geq 120 mIU/ml measles antibody titre.

For further details, please see Sample processing (HPA 1/1, WHO 2/1, WHO 3/1, WHO 4/1), Measurement of outcomes (SOP HPA 5/1, HPA 6/1, HPA 7/1)

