9.2 Secondary outcomes

For all infants:

- Geometric mean titres, pre-vaccination and at day 91;
- Seroconversion (defined as a change from Enzygost OD <0.1 to OD \ge 0.1 or PRNT from <120 to \ge 120 mIU/mL) measured in paired samples from day 0 and day 91;
- As covariates for inclusion in multivariable analyses: age; sex; day 0 antibody titre; study site; crying when vaccine given (aerosol arm only); presence of respiratory tract symptoms at time of vaccination (aerosol arm only). In addition, random subsets of 80 infants each with OD 0.1-0.2 and OD>0.2 at day 91 will be assessed for PRNT antibody concentrations to determine the relationship between PRNT and Enzygost optical densities/concentrations and validate the use of the cut-off of 0.1 for PRNT testing.

For infants in the day 28 blood sample subset or the day 364 blood sample subset:

- Geometric mean titres to describe evolution of antibody response at days 0, 28, 91, 364;
- Seropositivity at 364 days in infants with antibody titre \geq 120 mIU/ml at day 91.

10 Assessment of Safety

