When a unique study ID has been confirmed the person clicks the 'Randomization' button. The next screen gives the allocation as either, 'AEROSOL' or 'SUBCUTANEOUS'. The system records, in a separate database, the details of study site, child's names, Subject ID number, allocation, date and time of randomization. The randomization database will be maintained in Access as backend. This database will be maintained at the CDMC and the backup will be maintained at the backup server which is kept at the Pharmacology Department Museum (old name: Booshnam Moses Computing Center) (Refer SOP Randomization, No: 05 / 02).

SOP VEL 1/1:	Statistical Analysis Plan	Page 5 of 61	
September 11, 2012			

7.3 Blinding of Laboratory Staff:

Staff at the study sites and participants' parents will know which treatment has been given. To minimize bias in the assessment of immunogenicity outcomes, laboratory staff will not know the treatment allocation or the order of specimens that they will analyze.

In order to blind laboratory staff to the specimen collection time (day 0, day 28 day 91 or day 364) for the subjects, a single digit random number will be generated and concatenated with the subject ID. This is called the Lab Code. Thus a subject will have a unique Lab Code of 5 digits.

The laboratory will be provided with lists of 22 pairs (day 0 and day 91) of specimen Lab Codes, which will be randomly ordered. Similarly, for the specimens of children who will be followed up at day 28 and day 364, the laboratory will be provided with lists of randomly ordered Lab Codes.

8.0 Sample size:

8.1 Immunogenicity:

The sample size for the primary outcome is determined using the confidence interval (CI) approach, considering where the CI for the treatment effect lies with respect to a pre-specified margin of non-inferiority and the null effect (1).

Total to be enrolled, 2000. This number was based on the following assumptions:

- Significance 2.5%, one sided for non-inferiority, 5% for two sided superiority;
- Non-inferiority margin 5%;
- Power for non-inferiority 90% if true seropositivity is 90% in both arms;
- 20% loss to follow up by day 91, leaving 1600 available for primary analysis.

Sample size for immunogenicity subset:

Those selected for additional testing at day 28 or at day 364 will have ELISA and PRNT test results at these time points as well as at day 0 and 91.

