12.1. Efficacy Analyses: Immunogenicity

 Table 12.1.1A: Results of ELISA and PRNT, by study group, per-protocol analysis

	Baseline		Day	y 91
	AER	SC	AER	SC
	n=	n=	n=	n=
ELISA result (optical density)				
Median				
Interquartile range				
Min – Max				
Geometric mean titre				
95% CI	n=	n=	n=	n=
PRNT result (mIU/ml)				
Median				
Interquartile range				
Min – Max				
Geometric mean titre				
95% CI				

Legend:

AER – aerosol; SC - subcutaneous

For PRNT titre, includes subjects whose OD values are < 0.1 and all from Vadu site

SOP VEL 1/1:	Statistical Analysis Plan	Page 24 of 61
September 11, 2012		

	Baseline		Day 91	
	AER	SC	AER	SC
	n=	n=	n=	n=
ELISA result (optical density)				
Median				
Interquartile range				
Min – Max				
Geometric mean titre				
95% CI	n=	n=	n=	n=
PRNT result (mIU/ml)				
Median				
Interquartile range				
Min – Max				
Geometric mean titre				
95% CI				

Table 12.1.1B: Results of ELISA and PRNT, by study group, ITT analysis

Note: For PRN titre, the subjects whose OD values are < 0.1 and from Vadu site

12.1.2: Day 91 ELISA and PRNT results

Table 12.1.2A: Aerosol Group

	PRNT <120	PRNT >=120	PRNT not done	Total
Day 91 ELISA <0.1				
Day 91 ELISA >=0.1				
Day 91 ELISA Not done				
Total				

Legend:

Boxes highlighted in yellow represent results classified as seropositive at day 91

Phase II/III	WHO Measles Aerosol Vaccine	Protocol
Clinical Trial	Project	WHO/MAP/IN/002

Table 12.1.2B: Subcutaneous Group

	PRNT <120	PRNT >=120	PRNT not done	Total
Day 91 ELISA <0.1				
Day 91 ELISA >=0.1				
Day 91 ELISA Not done				
Total				

Legend:

Boxes highlighted in yellow represent results classified as seropositive at day 91

Table 12.1.3: Measles seropositive at day 91 post-vaccination (all infants) and difference in positivity between study arms

	AER n/N	AER%, 95% CI	SC n/N	SC%, 95% CI	Difference (AER- SC), 95% CI*
Seropositive at day 91					

Legend:

AER – aerosol; SC – subcutaneous;

* This difference is used to interpret non-inferiority, estimated by Wilson score method (5) (6).

Table 12.1.4A: Comparison of serological outcomes, by study group and time of sample collection: **Per Protocol cohort**

	AER		SC		Difference	
Time point	n	%	n	%	(AER-SC) 95% CI	
Day 0, seropositive						
Day 91, seropositive						
Day 91, seroconversion						

Legend:

AER – aerosol; SC - subcutaneous

Phase II/III	WHO Measles Aerosol Vaccine	Protocol
Clinical Trial	Project	WHO/MAP/IN/002

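### The -5-point rule is read on day-91 seropositivity in all infants, including those already seropositive at day 0, so a deficit among infants who needed the vaccine response can be diluted, and no margin is attached to the day-0 seronegative comparison

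*Supplement*

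**What the plan says.** Protocol 11.2.1 lists the sizing assumptions. They include "Significance 2.5%, one-sided for non-inferiority, 5% two-sided for superiority", a 5-point margin, 20% loss from 2000 enrolled to 1600 evaluable, and "Power for non-inferiority 90% if true seroconversion is 90% in both arms". The same list applies the -5% limit to the difference in the proportion seropositive at day 91.

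The protocol treats these as two outcomes. The primary one (9.1) is "Measles seropositivity at day 91 post-vaccination". Seroconversion is secondary (9.2) and is "measured in paired samples from day 0 and day 91". SAP 8.1 gives the assumption as "Power for non-inferiority 90% if true seropositivity is 90% in both arms", which matches the primary outcome.

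Nothing removes infants who already have antibody:
- Protocol 7.2 excludes prior vaccination ("Having received measles, measles-rubella or measles-mumps-rubella vaccine (with confirmation from vaccination card") and contraindications, but not day-0 seropositivity.
- SAP 11.2 admits to the per-protocol set every child with an interpretable day-91 result and no major deviation.
- SAP Table 12.1.3 covers all infants, and its legend says "This difference is used to interpret non-inferiority, estimated by Wilson score method".

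The plan expects some day-0 positives. It tabulates them (SAP Tables 12.1.4A/B, 17.3.1.1 and 17.3.2.1) and marks them as not applicable for seroconversion (Table 12.1.7).

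**The concern.** A vaccine comparison is informative in infants who must respond to become positive. An infant who has antibody at day 0 and would still have it at day 91 under either route adds the same result to both arms and pulls the difference towards zero. In a non-inferiority trial that pull favours the new product. Protocol 12.2 accepts the principle for natural boosting, which it says may affect the primary outcome, and sets out handling for measles cases. There is no counterpart for antibody present before vaccination.

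The existing secondary analyses do not fully close the gap. Protocol 5.4.1 promises a comparison by pre-vaccination titre. SAP 11.10 plans no subgroup analyses, and SAP 11.11 omits day-0 titre from the interactions. SAP 12.3 keeps it as a covariate, but Table 12.3.1 covers the aerosol arm only. The seroconversion rows of Tables 12.1.4A/B have a confidence interval but no margin and no reading rule.

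At stake is a pivotal licensure claim. The all-infant lower limit could clear -5% while the comparison in susceptible infants does not, and the plan does not say how that would be reported.

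**Working it through.** **1. The plan's own size.** Inputs from Protocol 11.2.1: 90% in both arms, margin 5 points, one-sided 2.5%, power 90%.

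n per arm = (1.960 + 1.282)² × 2 × 0.90 × 0.10 / 0.05² = 757, or 1514 in total, and 1514 / 0.8 = 1893 enrolled. With a continuity correction it is 797 per arm (1594). The stated 1600 evaluable (2000 × 0.8) is consistent with this. At 800 per arm, SE = √(0.18/800) = 0.015 and power = Φ(0.05/0.015 - 1.96) = 91.5%. Exact enumeration with the Newcombe-Wilson interval gives 91.3%. The result is the same whether the 90% is called seroconversion or seropositivity.

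**2. Dilution model.** Let b be the share seropositive at day 0 and k the fraction of these who remain positive at day 91 whatever the route; the rest are assumed to respond like the seronegatives. Then q = b × k, and
- p(SC) = q + (1-q) × 0.90
- p(AER) = q + (1-q) × 0.85
- all-infant deficit = (1-q) × 5 points
- seronegative deficit that equals 5 points overall = 5/(1-q)

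The 90% versus 85% is an assumption that puts the seronegative deficit exactly at the margin. The documents give neither b nor k, so a range is shown. Exact enumeration, 800 per arm, Newcombe-Wilson 95% interval:

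| q | SC | AER | Deficit seen (points) | P(declare NI) | 5/(1-q) (points) |
|---|---|---|---|---|---|
| 0 | 90.0% | 85.0% | 5.00 | 2.5% | 5.0 |
| 5% | 90.5% | 85.75% | 4.75 | 3.6% | 5.3 |
| 10% | 91.0% | 86.5% | 4.50 | 5.0% | 5.6 |
| 20% | 92.0% | 88.0% | 4.00 | 9.8% | 6.25 |
| 30% | 93.0% | 89.5% | 3.50 | 18.3% | 7.1 |

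Hand check at q = 10%: SE = √((0.91 × 0.09 + 0.865 × 0.135)/800) = 0.01576, and Φ(0.005/0.01576 - 1.96) = Φ(-1.64) = 5.0%.

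**3. Sensitivity to persistence.** If half persist (k = 0.5), b = 10%, 20% and 30% give q = 5%, 10% and 15%, and the probabilities are 3.6%, 5.0% and 7.1%. If none persist and all respond like the others (k = 0), q = 0 and there is no dilution (2.5%).

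**4. Effect on the planned primary test.** With a true 5-point deficit in all-infant seropositivity, the probability of declaring non-inferiority is 2.5% at each q examined from 0 to 30%. With 90% response among seronegatives in both arms, all-infant power is 91.3%, 92.4%, 93.5% and 95.5% at q = 0, 5, 10 and 20%.

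**5. Power of the same rule in day-0 seronegatives only.** This depends on b, because the number per arm is 800(1-b). At 90% in both arms:

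| b | n per arm | Power |
|---|---|---|
| 5% | 760 | 89.8% |
| 10% | 720 | 88.2% |
| 20% | 640 | 84.1% |

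**The case against.** The strongest reply is that the trial does what it says. The SAP background defines the 5% as the largest acceptable difference in the primary outcome. That outcome is seropositivity, and SAP 8.1 sizes the trial on it. The objective (Protocol 5.3.1) concerns infants eligible for a first dose, and Protocol 5.1 wants the setting of actual use, so an all-infant comparison is a legitimate target. Seroconversion differences with intervals are already planned in both analysis sets. This stands: the primary analysis should remain as it is.

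It also disposes of several stronger readings that a reader might infer:
- *The type I error exceeds 2.5%.* It does not for the endpoint that carries the margin (step 4). The higher figures in step 2 refer to a deficit defined in seronegatives, a hypothesis the plan does not test.
- *The stated 90% power is lost once about 5% are positive at day 0.* The planned all-infant test gains power as q rises. The falling figures in step 5 belong to a seronegative-only test that the plan does not contain.
- *The protocol's sizing term causes the dilution.* Dilution comes from the endpoint and population, and would remain if the word were corrected.
- *Every day-0 positive infant counts as a success.* Success needs a positive day-91 specimen; an infant whose antibody has been lost by then is a failure.

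What the reply does not answer is that the promised comparison by pre-vaccination titre has no two-arm analysis in the SAP with a reading rule, although day-0 serum is taken from every infant.

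**Conclusion.** The point holds in a limited form. The primary rule includes infants seropositive at day 0, and to the extent that they remain positive whatever the route, a deficit among seronegatives is reduced by the factor (1-q). The effect ranges from none, if no day-0 positives persist independently of route and they respond like the others, to a material one: a seronegative deficit exactly at 5 points would pass 5.0% of the time at q = 10% and 18.3% at q = 30%. These figures assume 800 per arm, 90% versus 85% in seronegatives, and values of q that the documents do not supply, so the actual size is unknown. Where there is an aerosol deficit and some persistence, the direction is towards non-inferiority.

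Sample size, primary-test power and the error rate for the stated endpoint are unaffected. The use of *seroconversion* in Protocol 11.2.1 is a separate wording inconsistency with SAP 8.1.

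**What to change.** 1. In Protocol 11.2.1, change *seroconversion* to *seropositivity* in the power assumption, to agree with 9.1 and SAP 8.1.
2. Keep the all-infant primary analysis. In SAP 11.1 and Table 12.1.4A, prespecify that the aerosol-minus-subcutaneous difference in day-91 seropositivity among per-protocol infants seronegative at day 0 is read against -5% as a key supportive analysis. Define day-0 status by the ELISA/PRNT rule of Protocol 9.1 and state the denominator. State also that a failure there is reported alongside the primary conclusion.

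The day-0 definition needs one reconciliation. Protocol 8.6.3.1 sends every specimen with OD below 0.1 to PRNT, SAP 6.1.1 names only day-91 specimens below 0.1 and all Vadu samples, and Table 12.1.7 allows for PRNT not done at baseline. The SAP should say how such infants are classified.

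Cost: one protocol word, a short SAP addition and a row beside an existing one. No new blood is needed, since day-0 serum is drawn from every infant and tested by ELISA; completing day-0 PRNT as the protocol describes may add laboratory work if the narrower SAP testing was followed. The supportive analysis has power of about 90%, 88% and 84% at 5%, 10% and 20% baseline seropositivity, so it may miss the limit by chance somewhat more often than the primary test.

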11.2.2 Safety

To estimate proportions with adverse events in aerosol and subcutaneous groups, the sample sizes above give acceptable precision.

Observed proportion	95% confidence intervals		
	N=100	N=800	N=1000
0%	0.00 - 3.6%	-	0.00 - 0.37%
1%	0.02 - 5.44%	0.43 - 1.96%	0.48 - 1.83%
2%	0.24 - 7.04%	1.15 - 3.23%	1.26 - 3.07%
5%	1.64 – 11.28%	3.60 - 6.75%	3.73 - 6.54%

With 1000 infants in each group the precision of estimation of adverse events is:

If no reactions are observed, the upper 95% confidence interval with a sample size of 1000 is 0.37%, or 1 in 270.

With 100 children sampled at random for follow up to 364 days, the precision for estimating the prevalence of rare events is low. If zero events are observed by day 364 the upper 95%CI will be 3.6% (1 in 28).

11.3 Criteria for the termination of the trial

The trial will be discontinued if a single SAE attributable to the aerosol vaccine is reported. The stopping rules have been determined by the DSMB following explicit written criteria (Appendix 2: Terms of Reference of the Independent Data Safety and Monitoring board).

11.4

11.5 Procedure for accounting for missing, unused and spurious data

11.5.1 Data handling and record keeping

See SOP VEL 2/1 for data management.

11.5.2 Data verification

See SOP VEL 2/1

Source documents including medical records and original laboratory results will be kept in a separate file at the investigator's office. Electronic CRFs will be downloaded with daily frequency at Vadu Rural Hospital dedicated computer and checked for completeness and accuracy. They will be sent to Vellore weekly. The SOP VEL 1/1 describes in detail the process for data collection including the use of audit trails to ensure data security. Printed copies of electronic CRFs will be kept in a room with limited access

11.5.3 Data entry

See SOP VEL 2/1

11.5.4 Data review

See SOP VEL 2/1

11.5.5 Data quality control

See SOP VEL 2/1

Besides range, consistency and missing value checks incorporated in the Study Builder software, further checks will be done using pre-tested syntax in SAS statistical software. If inconsistencies and out of range values are found, the Data Management Centre will produce a Query and Correction sheet for a subject with a query to the corresponding site PI. The PI or designee has to recheck the value and fill the correct value in the sheet with an authorized signature and send back to the Data Management Centre. Based on the filled Query and Correction sheet received from the Site, the data manager will update the Database.

11.5.6 Data sharing and analysis

Data will only be accessed by the sub-investigator in charge of data management and statistical analysis. The DSMB will receive quarterly unblinded reports. See SOP VEL 1/1

Outliers, missing values, and inconsistencies will be identified based on the Validation Check Specification document (in SOP VEL 2/1). If inconsistencies arise then the query will be raised at this level. Based on the query responses, corrections will be made in the original ACCESS database. Having completed all the corrections, the data will be exported to SAS software format. Data analysis will be carried out after all enquiries have been done and the database has been locked. Any data which is still missing after enquiries have been made will be dealt with as described below:

• Missing values

For the per-protocol (PP) dataset, missing values will be treated as missing at random. For the intention-to-treat (ITT) dataset, the analysis will also be run with imputed values for the missing values, for the best and worst case scenarios. In the best case scenario, we will assume no adverse events occurred and the individuals are seropositive. In the worst case scenario, we will assume an adverse event occurred and the individuals are seronegative.

• Outliers

For log 10 PRNT values [LPRNT], checks for outliers will be performed prior to the statistical analysis, as part of the data checking. The outliers will also be examined using standardized residuals >3 when looking at log 10 PRNT values [LPRNT].

12 Procedures for reporting any deviations from the original analysis plan

Any change in the planned analysis will be described and documented in the study report including the time (specifically whether prior to or after unblinding occurs) and reason for the change, the procedure used to decide on the change and the nature and content of the data available when the change was made.

12.1 Selection of subjects to be included in the analysis

12.1.1 Analysis sets

Primary analysis: per protocol (infants receiving the allocated vaccine and available for follow up at 91 days post-vaccination). For non-inferiority hypothesis, this is the conservative analysis;

Secondary analysis: intent-to-treat analysis (all infants randomised, analysed in the group to which they were allocated, irrespective of intervention received) of primary and secondary outcomes.

There will be one interim analysis for AE only (see section 12.1.3 below).

12.1.2 Immunogenicity

Primary analysis is to calculate the 2-sided 95%CI for the difference in proportion seropositive at day 91. If lower limit of difference greater than -5% then conclude non-inferiority. If lower limit of difference greater than 0% then conclude superiority.

Secondary analyses will include calculation of 95% confidence intervals for seropositivity, seroconversion and geometric means as well as multivariable logistic and normal errors regression adjusting for covariates.

Secondary analysis of factors associated with seroconversion/response, including:

- pre-vaccination titre
- Age (9m,10m,11m) (also look at interaction with intervention)
- Sex (also look at interaction with intervention)
- PHC
- Crying when vaccine given? (also look at interaction with intervention).
- (Another factor we considered before was acute respiratory infection)
- Explanatory variables for stratification of safety profile

